1.3.4 Risk of Incidental Findings

Since the MRI methods being tested are experimental, the MRI images will not be formally reviewed for incidental findings. However, if there is something that is of concern to the PI, then the PI will approach the IRB for guidance on how to proceed on a case-by-case basis. The consent will clearly state that the MRI images will not be evaluated for incidental imaging findings.

1.3.5 Protection Against Risk:

1. Subjects will stay on their prescribed oxygen levels while participating in the study. Oxygen will be discontinued briefly for 2 preparatory breaths prior to xenon inhalation, and then re-started after that.
2. Each subject will be allowed to read the consent form and ask questions. After all, the study subject questions are answered, and before any protocol-specified procedures are initiated, each subject will sign and date the consent form. A copy of the signed consent will be provided to the subject
3. Every effort will be made to keep your information confidential; however, this cannot be guaranteed
4. Duke University has formal education and certification procedures regarding research ethics (<https://irb.duhs.duke.edu/training-and-education>). All research personnel will complete these in full before entry into the protocol; the study's nature and risks will be reviewed with each subjects.

2 Study Objectives

The proposed research builds on the established sensitivity of Hyperpolarized ¹²⁹Xe MRI to obstructive (Ebner'17, restrictive (Rankine'20) and pulmonary vascular lung disease (Wang '19), features expected to be represented in the Covid-19 cohort. It further incorporates new understand of the possible role of myocardial injury in these recovered patients by combining cutting edge pulmonary and cardiac MRI.

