2.1 Primary Study Aims

- Aim 1 - Determine the cardiopulmonary structure-function abnormalities that characterize early phase COVID-19 recovery. We anticipate conducting ¹²⁹Xe and cardiac MRI in 13 recovering COVID patients recruited at their clinic visit 60 days' or longer post-discharge from their acute infection. We will recruit patients with new onset persistent and continued dyspnea and to characterize the interstitial, pulmonary vascular and myocardial abnormalities relative to a control population.
- Aim 2 – Characterize the evolution of cardiopulmonary abnormalities over 9 months. Patients will undergo repeat scanning 9 months later to assess changes in all regional parameters acquired from pulmonary and cardiac MRI, directly addressing the possible reversibility of cardiopulmonary limitations arising from “long COVID.”
- Aim 3 – Identify MRI features that predict physiologic outcomes and can alter treatment decisions. Patients will undergo PFTs and quality of life evaluations at 3, 6 and 9 months, as well as detailed clinical histories. These data will be used to understand which baseline imaging features are predictive of long-term quality of life and physiology outcomes as well as those that represent “treatable traits” that can be targeted for therapeutic intervention.

3 Study Design

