4.1 Inclusion Criteria

Diagnosis of post Coronavirus (COVID-19)

Inclusion Criteria

a. Age ≥ 18-year-old

CONFIDENTIAL

This document is confidential and the property of the Duke University.

- b. Tested positive for SARS-CoV2
- c. Willing and able to give informed consent and adhere to visit/protocol scheduled (consent must be given before any study procedures are performed)

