4.2 Exclusion Criteria

- a. Prisoners
- b. Pregnant, planning pregnancy or lactating
- c. Conditions that prohibit MRI scanning (metal in eye, claustrophobia, inability to lie supine).
- d. Medical or psychological conditions which, in the opinion of the investigator, might create undue risk to the subject or interfere with the subject's ability to comply with the protocol requirements

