6.2.2 Baseline (V0) (post COVID DX)

Informed consent will contain a statement that indicates that if a subject does not qualify to continue in the research study after the end of the screening, he/she will be withdrawn from

the study. Subjects that sign consent but do not pass the screening are considered enrolled in the research study and counted as withdrawn.

- After obtaining informed consent, the following data may be collected and documented on the source (paper or subject's electronic medical record):
 - Documentation of relevant patient history and symptoms – SOC
 - Medical History (including comorbid conditions) – SOC
 - Vital signs (temperature, heart rate, blood pressure, respiratory rate, and pulse oximetry) including weight and height - SOC
 - Including optional noninvasive, optical hemoglobin measurement
 - Concomitant Medications – SOC
 - PFT's - SOC
 - 6MWTs – SOC
 - Labs- SOC
 - Chest X-ray-SOC
 - MRI Imaging -SOC
 - Cardiac MRI
 - Completion of MRI screening form - research
 - MRI Imaging session – research
 - ^{129}Xe MRI
 - Urine pregnancy test (if applicable) performed outside the 48hrs window
 - Adverse event reporting – research
 - Standard dose CT - research

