^{129}Xe MRI metrics will include RBC/barrier, barrier/gas, RBC/gas, and several spectroscopic indices. Continuous data will be presented using the mean \pm SD if normally distributed and median with 25th and 75th percentiles otherwise. We are fortunate to be able to compare the findings in our images to a database of approximately 30 healthy reference subjects whom we have scanned to date. These subjects have undergone the same ^{129}Xe MRI protocol and were recruited with no histories of smoking or cardiopulmonary disease, FEV1>80%, FEV1/FVC>0.70 and DLCO >80%. For subjects to be included in the reference cohort they further had a ventilation defect percentage \leq 6%, (upper limit of normal VDP (Ebner '19)) as well as RBC/barrier \geq 0.45 (at TR=15 ms), and image SNR>5, based on the Rose criterion. Comparisons between these groups will use analysis of variance (ANOVA) methods or Kruskal-Wallis test as appropriate.

8 Safety and Adverse Events

8.1 *Overview*

As the sponsor of the study, Duke University Medical Center and the Principal Investigator shall be solely responsible for complying, within the required timelines, any safety reporting obligation to competent Health Authorities, IRB and any participating (co or sub) investigators, as defined in applicable laws and regulations. For this protocol, safety data include adverse events and special situations, including pregnancies.

8.2 *Management of Safety data*

This study has been designated as an interventional study. As such, all adverse events, special situations including pregnancies and product quality complaints will be reported as described in this protocol from the time a subject has signed and dated an Informed Consent Form (ICF) until 30 days after the last documented use of the study drugs (i.e., end of study (9 months)).

Adverse Event

An **adverse event** (AE) is any symptom, sign, illness, or experience that develops or worsens in severity during the study. Intercurrent diseases or injuries should be regarded as adverse events. Abnormal results of diagnostic procedures are considered to be adverse events if the abnormality:

CONFIDENTIAL

This document is confidential and the property of the Duke University.

- results in study withdrawal
- is associated with a serious adverse event
- is associated with clinical signs or symptoms
- is associated with Abnormal lab values
- leads to additional treatment or to further diagnostic tests

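### The healthy reference cohort excludes smoking and cardiopulmonary disease but the post-COVID group does not, so the unadjusted Aim 1 comparison can credit pre-existing disease to COVID-19

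*Combined protocol and SAP*

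**What the plan says.** **Comparator.** Section 7.2 draws on "a database of approximately 30 healthy reference subjects whom we have scanned to date". These subjects "were recruited with no histories of smoking or cardiopulmonary disease" and had FEV1 above 80%, FEV1/FVC above 0.70 and DLCO above 80%. They were then filtered on imaging results (ventilation defect percentage, RBC/barrier ratio, image SNR). Groups are compared by ANOVA or Kruskal-Wallis, and no adjustment is described.

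**Post-COVID group.** Section 4.1 asks for age 18 or over, "Tested positive for SARS-CoV2", and consent with willingness to follow the schedule. The only broad medical exclusion in Section 4.2 covers conditions that "might create undue risk to the subject or interfere with the subject's ability to comply with the protocol requirements". Neither section mentions prior lung disease, prior heart disease or smoking. Section 2 says that PFTs and the 6-minute walk do not guide enrolment.

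**Partial safeguards.**
- Aim 1 in Section 2.1 states: "We will recruit patients with new onset persistent and continued dyspnea". This is not repeated as an eligibility criterion.
- Section 2 says results will be stratified by ethnicity and by spirometric abnormality.
- Section 6.2.2 lists "Medical History (including comorbid conditions) – SOC" among data that may be collected at V0. Smoking is not named.
- Section 2 splits the 23 subjects into 13 with continuing respiratory symptoms and 10 competitive athletes.

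**The concern.** Aim 1 sets out to describe the abnormalities of COVID-19 recovery relative to controls. The two groups differ in COVID-19 history, but they may also differ in smoking and in earlier lung or heart disease, because only the controls were screened for these. Section 2 describes xenon MRI as sensitive to obstructive, restrictive and pulmonary vascular disease, "features expected to be represented in the Covid-19 cohort". Prior disease of those kinds can therefore register on the same measurements. No pre-COVID scan or PFT is required, so the study's own data may not show which came first. The sample size section also argues for a one-sided test on the ground that high barrier uptake is expected only after COVID-19. That argument leaves no room for prior disease as a source.

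At stake is the attribution in Aim 1: how much of an observed group difference can be called an effect of COVID-19. Aim 2 is affected less directly, through how a persisting abnormality is read.

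**Working it through.** **1. The plan's own figure.** Section 7.1 gives a 10-point difference in high barrier uptake, SD 10, 90% power, two-sided, n = 23. Alpha is not stated; 0.05 is assumed here.
- Normal approximation: n per group = 2 × (1.960 + 1.282)² × 10² / 10² = 21.01, rounded up to 22.
- Two-sample t-test: 22.02, rounded up to 23.

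The 23 is reproduced and is not in dispute. It supplies the 10-point yardstick used below.

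**2. Conditions side by side.**

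| Condition | Reference cohort (7.2) | Post-COVID group (2, 4.1, 4.2) |
|---|---|---|
| No smoking history | Required | Not mentioned |
| No cardiopulmonary disease | Required | Not mentioned |
| FEV1, FEV1/FVC, DLCO limits | Required | PFTs not used for enrolment |
| New-onset symptom | Not applicable | Aim 1 text only |

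**3. Size of the possible shift.** Suppose COVID-19 has no effect, and k subjects carry prior disease that raises high barrier uptake by D points. The group mean then shifts by k × D / n. Both k and D are assumptions; neither is in the documents.

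| k | D | n = 13 | n = 23 |
|---|---|---|---|
| 2 | 10 | 20/13 = 1.5 | 20/23 = 0.9 |
| 3 | 20 | 60/13 = 4.6 | 60/23 = 2.6 |
| 4 | 30 | 120/13 = 9.2 | 120/23 = 5.2 |

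The 13 is the number Aim 1 names; the 23 is the number Section 7.1 uses.

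**4. Effect on the false-positive rate.** Simulation of a t-test against 30 controls, with SD 10, two-sided 0.05, no COVID effect, 40,000 runs, and each subject having probability f of carrying a shift D.
- 13 subjects: f = 0.2 and D = 10 gives 9.6%; f = 0.3 and D = 20 gives 35.9%. Expected affected: 2.6 and 3.9.
- 23 subjects: f = 0.1 and D = 10 gives 6.5%; f = 0.2 and D = 20 gives 24.0%. Expected affected: 2.3 and 4.6.
- With f = 0 the rate is about 5% in both.

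**5. Aim 2.** Write a subject's value at V0 as P + C₀ and at V1 as P + C₁, where P is a stable prior abnormality and C the COVID-related part. The change is C₁ − C₀, so P cancels. Two effects remain. If an affected subject has little COVID-related abnormality to lose, the mean change is diluted. And the value at V1 still contains P, which can be read as COVID damage that did not resolve.

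**The case against.** **The plan has safeguards.** Stratifying by spirometric abnormality would place much obstructive or restrictive disease in its own stratum. Section 4.3 directs clinic staff to dyspnea persisting after COVID-19, and Aim 1 speaks of new onset. Ten of the 23 subjects are competitive athletes, in whom prior disease seems less likely, though no criterion says so. This stands in part and narrows the gap. It does not close it: spirometry at V0 cannot show when an abnormality began, it misses disease with normal spirometry, and a new symptom does not rule out an older condition or a smoking history.

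**The size is assumed.** This stands. A shift of 30 points is three times the plan's SD, and nothing in the documents supports that upper end. The range shows what could happen and is not an estimate.

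**Stronger readings.** A reader might infer that every subject with prior disease pushes the result towards a COVID effect, or that all such diseases produce the signature expected from COVID-19. The documents do not support either. Section 2 claims sensitivity to three classes of lung disease; it does not say that each raises high barrier uptake, and the title of one cited study speaks of distinct signatures across diseases. A reader might also infer that Aim 2 is biased as Aim 1 is; the cancellation in step 5 shows otherwise.

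**This is a small pilot.** Restricting 13 subjects further costs power. That also stands, and is why the restricted analysis is better placed beside the full cohort than in place of it.

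**Conclusion.** The point holds for Aim 1. The difference in entry conditions is explicit, no section removes it, and the comparison as written can attribute pre-existing disease to COVID-19. That it can do so follows from the text; how far it will do so cannot be known from the documents. Under the assumed 2 to 4 affected subjects with 10 to 30 points each, the false shift runs from 1.5 to 9.2 points on 13 subjects, or 0.9 to 5.2 on 23. At the upper end on 13 it approaches the 10-point difference the study is sized to detect; at the lower end on 23 it is minor.

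For Aim 2 the conclusion is limited to interpretation: diluted mean change, and a persisting prior abnormality that may be mistaken for irreversible COVID damage. The documents do not show that subjects with prior disease will be enrolled in any particular number, only that nothing in the eligibility criteria prevents it. The sponsor should make the change; it does not call the sample size into question.

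**What to change.** 1. **V0 data.** Record for every subject whether cardiopulmonary disease was present before COVID-19 and, as a separately named item, smoking history. Section 6.2.2 says only that comorbidity data may be collected, so both items should be made mandatory.
2. **Section 7.2.** Prespecify the Aim 1 comparison in subjects with neither history (the history rule the reference cohort met), reported alongside the full cohort. State that attribution to COVID-19, and the Aim 2 statement on reversibility, will rest on agreement between the two. Keep the spirometric stratification. Covariate adjustment is not a substitute: the controls include no one with either history, so there is no overlap to adjust over.
3. **Section 4.1.** Reconcile it with the new-onset wording of Aim 1 for the symptomatic cohort.

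**Cost.** A short amendment and two history items, with no new procedure. The restricted comparison loses precision. For a 10-point difference, SD 10, assumed two-sided alpha 0.05 and 30 controls, t-test power is about 84% with 13 subjects, 76% with 10 and 73% with 9. With so few subjects, the two analyses may also disagree by chance, so agreement should be judged on estimates and confidence intervals and not on significance alone.

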Although the initial presentation of patients with moderate to severe symptoms of COVID19 infections is dominated by respiratory symptoms, 10% go on to develop persistent post-infection symptoms which are thought to have an inflammatory etiology. Evidence suggests that pathologic activation of the inflammasome persists beyond the acute initial presentation that contributes to the persistent disabling symptoms characterized as “long-haul COVID”. For this trial, subjects will be eligible for enrollment if they are outpatients with a history of a laboratory confirmed diagnosis of COVID-19 infection, and after 60 days or longer. We will enroll 13 subjects who continue to have respiratory symptoms (i.e., cough, shortness of breath, dyspnea on exertion). An additional 10 subjects engaged in competitive sports and diagnosed with COVID-19 will also be enrolled. These subjects can be asymptomatic or mildly to moderately. Although rare, cardiac impairment has been documented in <2% of these

CONFIDENTIAL

This document is confidential and the property of the Duke University.

individuals. To our knowledge, XeMRI has not yet been studied in this specific patient subset.

The 6-minute walk test and PFTs will not be used to guide enrollment, but rather will be used in combination with XeMRI/cMRI to assess degree of functional impairment. We will stratify our results based on ethnicity and spirometric abnormalities from those subjects without these findings.

Existing data highlight significant racial and ethnic disparities with historically underserved minority populations (i.e., Black, LatinX) suffering disproportionately higher infection rates and more severe illness compared to Whites. This is reflected by the population enrolled in our RedCAP database and biorepository. As such 30% of subjects enrolled will be required to be from underserved communities.

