6.2.3 Visit 1 (V1) (6-9 months)

The following data may be collected and documented on the source (paper or subject's an electronic medical record):

- Documentation of relevant patient history and symptoms – SOC
- Medical History (including comorbid conditions) – SOC
- Vital signs (temperature, heart rate, blood pressure, respiratory rate, and pulse oximetry) including weight and height - SOC
 - Including optional noninvasive, optical hemoglobin measurement
- Concomitant Medications – SOC
- PFT's - SOC
- 6MWTs – SOC
- Completion of MRI screening form - research
- MRI Imaging session – research
 - Cardiac MRI
 - ^{129}Xe MRI
- Serum Pregnancy testing for a female of childbearing potential - research
 - Urine pregnancy test (if applicable) performed outside the 48hrs window
- Adverse event reporting – research
- Standard dose CT - research

CONFIDENTIAL

This document is confidential and the property of the Duke University.

7 Statistical Plan

7.1 *Sample Size Determination*

Power calculation: Based on the ^{129}Xe MRI metrics from our study (Wang, et al., 2019), we expect that we could detect an absolute difference of high barrier uptake of 10% between the post-COVID subjects and an existing cohort of healthy controls. We assume that with a standard deviation of 10% high barrier uptake within patients, and requiring a power of 90%, that a two-sided test would require a sample size of 23 to detect a difference. However, given that high-barrier uptake is expected only in the post-COVID group, a one-sided test suggests the proposed sample size has 99% power to detect a significant difference.

7.2 *Statistical Methods*

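### Section 7.2 compares post-COVID subjects with an existing healthy database and plans no age or sex adjustment, so an imbalance would be mixed with the COVID effect for any xenon metric that depends on age or sex

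*Combined protocol and SAP*

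**What the plan says.** Aim 1 (section 2.1) is to "characterize the interstitial, pulmonary vascular and myocardial abnormalities relative to a control population". No controls are enrolled. Section 7.2 takes them from a database of about 30 healthy subjects scanned before this study. Section 7.1 sizes the study to detect "an absolute difference of high barrier uptake of 10% between the post-COVID subjects and an existing cohort of healthy controls".

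The reference subjects were "recruited with no histories of smoking or cardiopulmonary disease" and met cut-offs for FEV1, FEV1/FVC and DLCO. The sentence beginning "For subjects to be included in the reference cohort they further had a ventilation defect percentage" adds limits on ventilation defects, RBC/barrier and image SNR. Age and sex are not among the criteria, and their distribution is not given.

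On the patient side, section 4.1 admits anyone aged 18 or over. Section 2 describes two sources. One is 13 subjects with continuing respiratory symptoms. The other is given as: "An additional 10 subjects engaged in competitive sports and diagnosed with COVID-19 will also be enrolled".

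The outcomes in section 7.2 are listed as: "MRI metrics will include RBC/barrier, barrier/gas, RBC/gas, and several spectroscopic indices". The test is "Comparisons between these groups will use analysis of variance (ANOVA) methods or Kruskal-Wallis test as appropriate". The only stratification, in section 2, is: "We will stratify our results based on ethnicity and spirometric abnormalities from those subjects without these findings".

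**The concern.** The groups are neither randomised nor matched, and they come from different sources: a post-COVID clinic, competitive sport, and a volunteer database. Nothing in the design makes their age or sex alike. The phrase about ANOVA methods could stretch to a model with covariates, but none is named, and a Kruskal-Wallis test cannot take one. Stratifying by ethnicity and spirometry does not deal with age or sex.

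At stake is the reading of Aim 1. If a metric changes with age or differs by sex, a demographic difference could be reported as an interstitial or vascular abnormality of COVID recovery. A difference in the other direction could conceal a real one. A metric with no such dependence is unaffected.

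**Working it through.** **1. The plan's own figure.** Inputs from section 7.1: difference 10 points, SD 10 points, power 90%, two-sided. Alpha is not stated, so 0.05 is assumed. A two-sample t calculation gives power 0.8997 at 22 per group and 0.912 at 23 per group, so the stated 23 reproduces. Against about 30 reference subjects, two-sided power for a 1 SD difference is 94.3% with all 23 and 83.7% with the 13 symptomatic subjects.

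**2. False-positive rate when the groups differ only demographically.** Let b be the mean shift, in SD units, caused by age or sex alone, with no COVID effect.

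- Standard error = √(1/n₁ + 1/n₂), which is 0.277 for 23 v 30 and 0.332 for 13 v 30.
- Noncentrality = b / standard error. At b = 0.5 this is 1.80 (df 51) and 1.51 (df 41).

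| b (SD, assumed) | 23 v 30 | 13 v 30 |
|---|---|---|
| 0 | 5% | 5% |
| 0.1 | 6.4% | 6.0% |
| 0.25 | 14.3% | 11.4% |
| 0.5 | 42.5% | 31.3% |

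In simulation Kruskal-Wallis is close to these: about 6%, 14% and 41% for 23 v 30, and 6%, 11% and 29% for 13 v 30.

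**3. The pooled figure depends on how each subgroup differs.** Assume a correlation of 0.5 between metric and age, and an age gap of 1 SD between the symptomatic subjects and the reference. The symptomatic shift is 0.5 × 1 = 0.5 SD. The pooled shift is 0.5 × (13 × symptomatic gap + 10 × athlete gap) / 23.

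| Athletes' age gap (assumed) | Pooled shift | 23 v 30, simulated | 13 v 30 |
|---|---|---|---|
| Same, +1 SD | 0.5 × 23/23 = 0.50 SD | about 41% | about 30% |
| None | 0.5 × 13/23 = 0.28 SD | about 15% | about 30% |
| Opposite, −1 SD | 0.5 × 3/23 = 0.07 SD | about 4% | about 30% |

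I reran these three cases (10,000 replicates, normal data). The t-test gave 43%, 17% and 4% for 23 v 30, and Kruskal-Wallis gave 41%, 16% and 4%. An ordinary linear model on group, age and sex gave about 5% for both contrasts in every case. Those data were generated by the same linear age model that was then fitted, so this does not test non-linear age effects or poor overlap in age.

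**4. The cost of adjusting.** If age and sex explain a share R²g of group membership and R²y of outcome variance, the noncentrality is multiplied by √(1 − R²g) / √(1 − R²y). Both shares are assumptions.

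| Case, 1 SD difference | 23 v 30 | 13 v 30 |
|---|---|---|
| Unadjusted | 3.61 → 94% | 3.01 → 84% |
| R²g = 0.3, R²y = 0 | 3.61 × 0.837 = 3.02 → 84% | 3.01 × 0.837 = 2.52 → 69% |
| R²g = 0.3, R²y = 0.25 | 3.02 / 0.866 = 3.49 → 93% | 2.52 / 0.866 = 2.91 → 81% |

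**The case against.** Everything about size is conditional: no dependence on age or sex is shown, and no imbalance is shown. This stands. A reader might infer that the planned test has a false-positive rate above 40%. The documents do not support that. The figure needs a large assumed shift in the same direction in both patient subgroups, and with opposite gaps the pooled rate is not inflated at all.

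Section 7.1 anticipates high-barrier uptake in the post-COVID group alone. If that is right, healthy people show little of it whatever their age or sex, and an imbalance shifts the one sized metric little. This is an expectation and not evidence, but it makes the concern weaker for that metric than for RBC/barrier, barrier/gas and RBC/gas.

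Both groups have the same xenon imaging protocol, which limits the technical bias that a non-concurrent control usually raises. It does nothing for demographic differences.

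Section 4.3 calls the study a pilot, and section 1 puts feasibility and value first. Aims 2 and 3 concern change within patients and prediction from baseline features, so the reference comparison does not enter them. That limits the reach of the point, but Aim 1 is still a patient-versus-control contrast with a formal power calculation.

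Finally, an ANOVA framework can carry covariates. It can, but an unnamed covariate is not prespecified.

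**Conclusion.** The omission is certain: there is no age or sex matching, no adjustment, and no covariate named for the Aim 1 xenon comparison. Its effect is unknown, because the documents neither state nor exclude a dependence on age or sex and give no demographics for the reference database. Under the assumptions in the working, the symptomatic-versus-reference contrast, which is the one Aim 1 names, is the more exposed, at about 30% false positives. The pooled contrast ranges from no inflation to about 41%. It would go too far to say that the groups are imbalanced or that Aim 1 is confounded.

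The point covers the xenon metrics only, since section 7.2 describes only xenon imaging in the reference subjects. Selection of the reference cohort on RBC/barrier of at least 0.45, itself a listed outcome, is a separate issue that age and sex adjustment does not cure. The change is worth making because it is cheap, not because a bias has been shown.

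**What to change.** In section 7.2, and in the matching text of the Study Summary:

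- Make the main xenon comparison a linear model (ANCOVA) of each metric on group (symptomatic, athlete, reference), age and sex.
- Report adjusted differences with 95% confidence intervals for symptomatic v reference (Aim 1) and for all post-COVID v reference.
- Show the unadjusted ANOVA or Kruskal-Wallis result alongside.
- Tabulate age and sex by group. Where age ranges do not overlap, restrict the contrast to the overlapping range or report it as descriptive.
- Robust standard errors are an option where variances differ, not a requirement.

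The cost is a few sentences of plan text, a few lines of code and no new patient procedure. Age and sex must be retrieved for about 30 existing records. That they are held is an inference: the FEV1 and DLCO cut-offs read as percent predicted. Adjustment also costs power if age and sex separate the groups without explaining the outcome, as shown in the last table of the working.

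### Section 7.2 names no unequal-variance comparison for a smaller post-COVID group against about 30 screened controls; if the controls vary less, as is likely for high barrier uptake, the named tests can exceed their nominal 5%

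*Combined protocol and SAP*

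**What the plan says.** Section 7.2 gives the whole comparison method in one sentence: "Comparisons between these groups will use analysis of variance (ANOVA) methods or Kruskal-Wallis test as appropriate". The synopsis says the same. The nearby sentence on normality governs how data are summarised (mean and SD, or median and quartiles). No variance check, unequal-variance method or interval for the difference is specified.

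The comparison group is a "database of approximately 30 healthy reference subjects", restricted to non-smokers without cardiopulmonary disease and with normal spirometry and DLCO. Section 7.2 adds imaging limits ("For subjects to be included in the reference cohort they further had a ventilation defect percentage" of at most 6%, RBC/barrier of at least 0.45, SNR above 5). RBC/barrier is also one of the outcomes.

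The post-COVID group has no such limits (sections 4.1 and 4.2) and is mixed. Section 2 states "We will enroll 13 subjects who continue to have respiratory symptoms" and "An additional 10 subjects engaged in competitive sports and diagnosed with COVID-19 will also be enrolled", and says of the athletes "These subjects can be asymptomatic or mildly to moderately". Aim 1 in section 2.1 concerns the 13.

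Section 7.1 assumes an SD of 10% for high barrier uptake within patients and a difference of 10%, and concludes that "a two-sided test would require a sample size of 23 to detect a difference" with 90% power. It then argues for a one-sided test "given that high-barrier uptake is expected only in the post-COVID group".

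**The concern.** Classical ANOVA pools the group variances. When the smaller group is the more variable one, the larger and narrower group dominates the pooled variance. The standard error of the difference is then too small and the test rejects too often. Kruskal-Wallis avoids the pooled SE, but as a test of location it also relies on distributions of similar shape and spread.

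The patient group is the smaller one in either comparison (13 or 23 against about 30). If high barrier uptake is essentially a post-COVID finding, a percentage bounded at zero has little room to vary among controls. At stake is the error rate of the Aim 1 comparison with controls, and the width of any confidence interval later attached to the difference.

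**Working it through.** **Inputs.** Patient n is 13 or 23 (sections 2, 2.1 and 7.1) and control n is 30 (section 7.2). Patient SD is 10 (section 7.1, high barrier uptake). Control SD is not stated and is assumed here: 10 (equal), 5 and 2. Alpha is not stated; 5% two-sided is assumed.

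**The plan's own figure.** With difference 10 and a common SD of 10, the exact two-sample t calculation gives power 0.8997 at 22 per group and 0.9125 at 23 per group. The stated 23 is therefore reproduced as a per-group size under equal variance. The stated 99% one-sided power is nearly reached at 23 v 30 with a common SD (97.5%, normal approximation), and is exceeded if the control SD is 5 (99.7%). Neither figure reveals the control SD.

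**Standard error of the difference.**

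- True SE = √(100/n + s²/30), where n is the patient group size and s the control SD.
- Pooled SE = √{[(n−1)·100 + 29·s²]/(n+28) · (1/n + 1/30)}.

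For 13 v 30 with s = 5:

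- true SE = √(7.692 + 0.833) = 2.92;
- pooled variance = (1200 + 725)/41 = 46.95, so pooled SE = √(46.95 × 0.1103) = 2.28;
- ratio 0.78, so 22% too small.

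The other cases:

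| Comparison | Control SD | True SE | Pooled SE | Shortfall |
|---|---|---|---|---|
| 13 v 30 | 5 | 2.92 | 2.28 | 22% |
| 13 v 30 | 2 | 2.80 | 1.88 | 33% |
| 23 v 30 | 5 | 2.28 | 2.10 | 8% |
| 23 v 30 | 2 | 2.12 | 1.87 | 12% |

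**Rejection rate under equal means** (simulated, normal data, 100,000 runs per case or more, nominal 5% two-sided):

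| Comparison | Control SD | ANOVA | Kruskal-Wallis | Welch |
|---|---|---|---|---|
| 13 v 30 | 10 | 5% | 5% | 5% |
| 13 v 30 | 5 | 13% | 9% | 5% |
| 13 v 30 | 2 | 20% | 13% | 5% |
| 23 v 30 | 10 | 5% | 5% | 5% |
| 23 v 30 | 5 | 7% | 7% | 5% |
| 23 v 30 | 2 | 9% | 10% | 5% |

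The Kruskal-Wallis column applies when that test is read as a test of location.

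**Opposite direction.** If patients were half as variable as controls on some metric, the named tests would be conservative: ANOVA 1.4% and Kruskal-Wallis 2.7% at 13 v 30, and 3.6% and 4.7% at 23 v 30.

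**Cost of Welch when SDs are equal** (difference 10, SD 10): power is 82.1% against 83.6% for the pooled test at 13 v 30, and 94.2% against 94.3% at 23 v 30.

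**RBC/barrier.** Suppose the 0.45 cut removes 5%, 10% or 20% of an otherwise identical normal population (assumed; the share is not stated). The patient-to-control SD ratio is then only 1.11, 1.19 or 1.31, but the control mean also shifts. At 23 v 30, ANOVA rejects 7.1%, 12.0% or 29.4% of the time, and Welch still rejects 6.8%, 11.2% or 26.8%.

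**The case against.** The strongest reply is that the unequal spread is inferred. Section 7.1 gives one SD, for patients and for one metric. The sentence about where high barrier uptake is expected concerns its occurrence, not its variance. The sample size of 23 fits a common SD, and at equal SDs nothing is wrong. This stands. A reader might infer that the plan itself declares the spreads different, or that its false-positive rate does exceed 5%. The documents support neither; the excess is conditional on the assumed control SD.

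A reader might also infer that screening narrows every metric. Of the listed metrics only RBC/barrier is itself a filter, and trimming alone gives SD ratios well short of the 2 to 5 used in the tables. The SD of 10 cannot be carried over to the other metrics.

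Nor are the planned summaries wrong. Group SDs and quartiles are unaffected by pooling, and the plan promises no interval for the difference. The understated SE matters for the test and for any interval added later.

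The equal-means null is stylised for high barrier uptake, because patients with a mean near zero could hardly have a normal distribution with SD 10. The SE shortfall does not depend on that null. With skewed data at 13 v 30 (means 12 and 2, SDs 10 and 2), nominal 95% intervals cover about 78% to 79% pooled and 92% with Welch. In that same case, however, both tests reject at least 99% of the time, so the test conclusion would not change.

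Finally, the wording in 7.2 is broad enough to include a Welch ANOVA. It does not exclude one, but it leaves the choice open until the data are seen.

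**Conclusion.** The point holds as a conditional one. Section 7.2 names no method that is safe under unequal variance, and the group sizes are in the unfavourable arrangement if patients are more variable. That is likely for high barrier uptake, possible for RBC/barrier, and not addressed by the documents for the other metrics.

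With patient SD 10 and an assumed control SD of 2 to 5, the effect is serious for the 13-subject Aim 1 comparison (ANOVA about 13% to 20%, Kruskal-Wallis about 9% to 13%). It is modest for all 23 (about 7% to 9% and 7% to 10%). At equal SDs it vanishes.

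In a small single-site pilot, with a remedy that costs only wording, this is a cheap improvement and not a must-fix. It would be a mistake to read Welch as making the control comparison sound: it repairs the variance problem only, and the mean shift from selecting controls on RBC/barrier remains.

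**What to change.** In section 7.2 and the synopsis, name the Welch (unequal-variance) t-test, or Welch ANOVA where more than two groups are compared, as the comparison for each metric. Report the mean difference with its Welch 95% CI. Keep a rank-based test as a sensitivity analysis; which one is a matter of preference.

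It would help to state the reference cohort's SD for each metric. Those subjects have already been scanned, so the assumed range above could be replaced by a known value.

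Treat the selection of controls on RBC/barrier separately, as a source of bias that no choice of test removes.

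The cost is wording, plus a power loss of at most about 1.5 points (13 v 30) if the variances prove equal.
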